#### **17.1.4 Vital Signs**

A descriptive statistics summary of vital signs and derived changes from baseline will be provided by cohort and treatment, and scheduled timepoint. Baseline is defined as measurement prior to initiation of treatment on Day 1 of each treatment period, where available.

All vital signs data will be listed by subject.

#### **17.1.5 Electrocardiograms**

A descriptive statistics summary of 12-lead ECG parameters and derived changes from baseline will be provided by cohort and treatment, and scheduled timepoint. Where triplicate ECGs are taken, the average parameter values of the triplicates will be reported. Baseline is defined as the average of triplicate measurements prior to initiation of treatment on Day 1 of each treatment period, where available.

A summary table for QTcF categories ( $\leq 450$  msec,  $>450$  to  $\leq 480$  msec,  $>480$  to  $\leq 500$  msec, and  $> 500$  msec) by cohort and treatment, and timepoint will be presented. The table will also summarize the number and percentage of subjects with change from baseline for categories of  $\leq 30$  msec, 30 msec to  $\leq 60$  msec, and  $> 60$  msec.

All 12-lead ECG parameters, physician's conclusions, and corresponding abnormalities will be listed by subject.

Descriptive statistics will be provided to summarize mean ECG parameters (observed and changes from baseline) by treatment, visit, and scheduled time.

#### **17.1.6 Cardiac Telemetry**

A listing of the cardiac telemetry data will include the start and stop times of telemetric observation, the occurrence of any arrhythmia or tachycardia of Grade 2 or higher (i.e. heart rate greater than 115 beats per minute), and the clinical evaluation of clinical significance of any arrhythmia or tachycardia.

#### **17.1.7 Echocardiograms**

A listing of the echocardiogram data will include the date and time of the assessment, the ejection fraction, and any clinical finding confirmed by cardiologist.

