AEs will be mapped to a Medical Dictionary for Regulatory Activities (MedDRA) preferred term (PT) and system organ classification (SOC). Any event reported on the subject's study record that occurs on or after the initiation of study drug is defined as treatment emergent. Additionally, it is assumed that an AE that is reported to have started on Day 1 of a given treatment period without an associated onset time may have occurred after the initiation of study drug. Hence, AEs occurring on Day 1 with no associated onset time will be assumed to be treatment emergent. The occurrence of treatment-emergent AEs will be summarized by cohort and treatment assignment using MedDRA PT, SOC, and severity. Separate summaries of treatment-emergent SAEs and AEs considered to be related to study drug will be generated. All AEs will be listed for individual subjects showing both verbatim and preferred terms.

Descriptive summaries of vital signs, ECG parameters (12-lead and telemetry), ECHOs, and clinical laboratory results will be presented separately for each cohort by study visit and treatment assignment. Laboratory abnormalities will be graded according to the modified DMID criteria (2014) in APPENDIX A.

Physical examination results will be presented in listings.

Concomitant medications will be coded using the World Health Organization Dictionary. These data will be summarized by cohort and treatment assignment.

Pharmacokinetics:

Concentrations of galidesivir will be determined by validated plasma and urine assays and will be summarized by treatment and displayed in figures. Plasma PK parameters for each subject will be estimated over the sampling interval using noncompartmental analysis (Phoenix WinNonlin Version 7.0 or higher, Certara) and summarized by treatment group using descriptive statistics. The amount and percentage of galidesivir excreted in the urine will be assessed at all doses.

Dose proportionality will be evaluated over all doses and will be based upon AUC_{inf} , AUC from time 0 to time “t” (AUC_t), and C_{max} using both the power model and the analysis of variance method.

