6. ENDPOINTS

6.1. Primary Endpoints

- Safety and tolerability parameters including AEs and SAEs, laboratory abnormalities, vital signs, ECGs, ECHOs, cardiac telemetry, and PE findings

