12.3.1.3. Analysis of Safety Variables

AEs will be mapped to a Medical Dictionary for Regulatory Activities (MedDRA) preferred term (PT) and system organ classification (SOC). Any event reported on the subject's study record that occurs on or after the initiation of study drug is defined as treatment emergent. Additionally, it is assumed that an AE that is reported to have started on Day 1 of a given treatment period without an associated onset time may have occurred after the initiation of study drug. Hence, AEs occurring on Day 1 with no associated onset time will be assumed to be treatment emergent. The occurrence of TEAEs will be summarized by cohort and treatment assignment using MedDRA PTs, SOCs, and severity. Separate summaries of treatment-emergent SAEs and AEs considered to be related to study drug will be generated. All AEs will be listed for individual subjects showing both verbatim and preferred terms.

Descriptive summaries of vital signs, ECG parameters (12 lead and telemetry), ECHOs, and clinical laboratory results will be presented separately for each cohort by study visit and treatment assignment. Laboratory abnormalities will be graded according to the modified DMID criteria ([APPENDIX A](#)).

Any graded abnormality that occurs following the initiation of study drug and represents at least one grade increase from the baseline assessment is defined as treatment emergent. The number and percentage of subjects experiencing treatment-emergent graded toxicities will be summarized by treatment group. Laboratory toxicity shifts from baseline to post-baseline assessments will be summarized by treatment group.

PE results will be presented in listings. Changes in PE results that are AEs will be reported in AE tables.

Concomitant medications will be coded using the World Health Organization (WHO) Dictionary. These data will be summarized by cohort and treatment assignment.

Subjects receiving placebo will be pooled and reported together across cohorts.

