#### 5.1.1 Primary Endpoints

The primary endpoints of the study are:

- Safety and tolerability parameters including adverse events (AEs) and serious adverse events (SAEs), laboratory abnormalities, vital signs, electrocardiograms (ECGs), echocardiograms (ECHOs), cardiac telemetry, and physical examination (PE).

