## 7.0 Overview of Planned Analysis

### 7.1 Changes from Protocol

There are no changes from the protocol.

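### The protocol promises descriptive summaries of ECHO and telemetry, but the SAP plans listings only and declares no change, so ejection fraction is summarised nowhere by dose

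*SAP*

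**What the plan says.** **Protocol.** Section 6.1 defines the primary endpoint as "Safety and tolerability parameters including AEs and SAEs, laboratory abnormalities, vital signs, ECGs, ECHOs, cardiac telemetry, and PE findings". Section 12.3.1.3 sets the output: "Descriptive summaries of vital signs, ECG parameters (12 lead and telemetry), ECHOs, and clinical laboratory results will be presented separately for each cohort", broken down by study visit and treatment assignment. The synopsis repeats the commitment: "Descriptive summaries of vital signs, ECG parameters (12-lead and telemetry), ECHOs, and clinical laboratory results will be presented separately for each cohort". Among the safety assessments named there, only the physical examination is sent to listings: "PE results will be presented in listings".

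**SAP.** Section 5.1.1 names ECHOs and cardiac telemetry in the primary endpoint, as the protocol does. The planned output for each is a listing. For ECHO (17.1.7): "A listing of the echocardiogram data will include the date and time of the assessment, the ejection fraction", plus any finding confirmed by a cardiologist. For telemetry (17.1.6): "A listing of the cardiac telemetry data will include the start and stop times of telemetric observation", plus any arrhythmia or Grade 2 or higher tachycardia and the judgement of its clinical significance. Appendix 3 carries these as Listings 16.2.11 and 16.2.12. On departures from the protocol, SAP 7.1 says "There are no changes from the protocol", while SAP 3.0 says that substantial differences from the protocol's statistical considerations are identified.

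**The concern.** The protocol authors separated what would be summarised from what would be listed, and put ECHO and telemetry in the first group. The SAP moves both to the second group without saying so. A reader who relies on SAP 7.1 would expect tables that do not exist.

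The consequence differs between the two measures. Telemetry here is alarm-based monitoring with no scheduled numeric variable. Ejection fraction is a number, obtained before dosing and again on Day 4 (Protocol 11.3.1.6). The protocol has a reason to look at it: Section 4.2.3 lists the heart among the rat toxicity sites, and Section 4.5 says the cardiomyopathy risk is not clear from animal studies and names ECHO as one of the ways to monitor it. A shift in ejection fraction that stays within the normal range need not be called an abnormality, and would then appear only as individual values in a listing.

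**Working it through.** No stated figure has to be reproduced; the question is which outputs exist.

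**1. Commitment against output**

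| Measure | Protocol 12.3.1.3 and synopsis | SAP text | Section 14.3 output in SAP Appendix 3 |
|---|---|---|---|
| Vital signs | Summary | Summary (17.1.4) | 14.3.6 |
| 12-lead ECG | Summary | Summary (17.1.5) | 14.3.7.1, 14.3.7.2 |
| Laboratory | Summary | Summary (17.1.3) | 14.3.4, 14.3.5.1 to 14.3.5.3 |
| Telemetry | Summary | Listing (17.1.6) | None |
| ECHO | Summary | Listing (17.1.7) | None |
| Physical examination | Listing | Listing (17.1.8) | None |

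Section 14.3 holds 4 adverse event tables (14.3.1.1 to 14.3.1.4), 3 listings (14.3.2, 14.3.3, 14.3.4), 3 laboratory tables, 1 vital signs table and 2 ECG tables: 4 + 3 + 3 + 1 + 2 = 13. None covers ECHO or telemetry. Physical examination agrees between the documents; ECHO and telemetry do not.

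**2. What still reaches a summary table.** Protocol 11.3.1.5 has clinically relevant telemetry abnormalities recorded and graded as AEs. Protocol 11.3.1.6 does the same for new post-baseline ECHO abnormalities confirmed by the cardiologist. SAP 17.1.1 then tabulates TEAEs by cohort and treatment, by severity and by relationship. What remains unsummarised is ejection fraction, its change, and telemetry events judged not clinically relevant.

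**3. Whether another planned review fills the gap.** The dose escalation review in Protocol 7.1 names laboratory, AE, vital sign, ECG (12-lead and telemetry) and examination data, not ECHO. The itemised interim safety report in Protocol 11.5.2 does not name ECHO either, although that section calls for all available safety data and allows narratives. SAP 9.1.3 says which statistics to use for a continuous variable, but it does not create an ECHO table.

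**4. How many subjects a table would hold.** As planned, 6 active per dose and 4 cohorts x 2 = 8 pooled placebo. These are ceilings without replacements. Protocol 8.5 requires only 5 evaluable active subjects per cohort, with evaluability judged through 24 hours, which is before the Day 4 ECHO.

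**5. How precise it would be.** For the difference in mean change between one dose and pooled placebo, with a common SD, the 95% CI half-width is t x SD x sqrt(1/n1 + 1/n2).

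- 6 versus 8: 2.179 x sqrt(1/6 + 1/8) x SD = 2.179 x 0.540 x SD = 1.18 SD.
- 5 versus 8: 2.201 x sqrt(1/5 + 1/8) x SD = 2.201 x 0.570 x SD = 1.25 SD.

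The documents give no SD for change in ejection fraction. If it is assumed to be 4 to 6 percentage points, the half-width is 4.7 to 7.1 points with 6 subjects and 5.0 to 7.5 points with 5.

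**The case against.** The best defence is that little of clinical importance is lost. Findings that matter become AEs and are tabulated. A telemetry table restricted to clinically relevant events would largely repeat the TEAE tables. A listing is not improper for a component of the primary endpoint, since the protocol itself assigns examination findings to one. The SAP supersedes the protocol's statistical section and need flag only substantial differences; whether a table or a listing is substantial in a descriptive Phase 1 study can be argued. With two ECHOs in 32 subjects, the listing has about 64 ejection fraction values, which can be read through. The table shells are in a separate document that was not available for this review.

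Most of this stands for telemetry. It does not answer the ejection fraction part: the AE route catches abnormalities, not numeric shifts, and the protocol promised a summary. Small numbers are no reason to omit one either, because the SAP tabulates vital signs, 12-lead ECG and laboratory data at the same sizes. Even if listings were a deliberate choice, SAP 7.1 should say so.

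A reader might also make something of the absence of both measures from the bullet list in SAP 17.1. That is editorial: each has its own subsection and listing, and no output is lost through it.

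**Conclusion.** The mismatch is confirmed. Two measures promised as descriptive summaries are planned as listings, and the SAP declares no change. The gap that matters is one variable: ejection fraction and its change are summarised nowhere by dose.

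Two stronger conclusions are tempting and are not supported. The first is that two components of the primary endpoint have no route into any summary; the AE rules in Protocol 11.3.1.5 and 11.3.1.6 provide one for the findings judged relevant. The second is that a by-dose table would reveal a small fall in ejection fraction. At 6 against 8 subjects the interval half-width is about 1.18 SD, so a small shift at one dose could not be reliably separated from noise. The table makes groups comparable at a glance and delivers what the protocol promised; it does not supply detection power.

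This is a minor point about completeness of reporting. No hypothesis test, sample size or dosing decision depends on it. The precision figures assume a common SD, and the ranges in points rest on the assumed SD of 4 to 6.

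**What to change.** - **Ejection fraction.** Add to SAP 17.1.7 and Appendix 3 one table of observed values and change from the last pre-dose ECHO (the baseline rule in SAP 9.2.1), with n, mean, SD, median, minimum and maximum, by dose and pooled placebo. Base change on subjects with both ECHOs, show that n, and state that the table is descriptive with limited precision per dose.
- **Two footnotes to that table.** Protocol 10.1.1 lets backup subjects carry a screening ECHO into a later cohort, so mark baselines older than 28 days. The protocol puts the post-dose ECHO on Day 4 and SAP Appendix 2 puts it on Day 3, so reconcile the visit label before programming.
- **Telemetry.** Either count subjects with any arrhythmia or Grade 2 or higher tachycardia by dose and pooled placebo, which the listing already captures, or keep the listing and correct SAP 7.1 to declare and explain the departure.
- **Tidying.** Add both measures to the SAP 17.1 list.

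The cost is one or two small tables from data already collected, plus one sentence in SAP 7.1 if the telemetry listing is kept.

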#### **17.1.8 Physical Examination**

All physical examination data will be listed by subject.

---

## Appendix 1: Glossary of Abbreviations

### Glossary of Abbreviations:

AE	Adverse event
ADaM	Analysis data model
AUC	Area under the concentration-time curve
AUC inf	Area under the concentration versus time curve extrapolated to infinite time
AUC t	Area under the concentration time curve from time 0 to time t (hours)
AUC% extrap	Percentage of AUC extrapolated between AUC t and AUC inf .
BQL	Below the quantifiable limit
CI	Confidence interval
C last	Concentration observed at the last quantifiable time point.
CL/F	Apparent oral clearance after administration of the drug
C max	Maximum plasma concentration.
CSR	Clinical study report
CRU	Clinical research unit
CV	Coefficient of variation
DMID	Division of Microbiology and Infectious Disease
ECG	Electrocardiogram
eCRF	Electronic case report form
EDS	Early Development Services
LSM	Least squares means
Max	Maximum
MedDRA	Medical Dictionary for Regulatory Activities
Min	Minimum
PK	Pharmacokinetic
QC'd	Quality controlled
SAP	Statistical analysis plan
SAE	Serious adverse event
SD	Standard deviation
TEAE	Treatment-emergent adverse event
TFL(s)	Tables, figures and listings
T lag	Elapsed time from dosing at which analyte was first quantifiable in a concentration vs. time profile
T last	Time of C last
T max	Time of C max

---

$T_{1/2}$	Terminal phase half-life expressed in time units
$V_z/F$	Apparent volume of distribution of the drug.
WHO	World Health Organization
$\lambda_z$	Terminal elimination rate constant

## Appendix 2: Schedules of Assessments from Protocol

### Schedule of Assessments

Assessment	Screening	In Clinic (CRU) Study Period						Return to CRU for PK Sample	Follow-up or Early Termination Visit
	Day -28 to -2	Day -1 (Admission)	Day 1 Baseline (Pre-dose)	Day 1 (Post dose)	Day 2	Day 3	Day 4 (Discharge)	Day 5, Day 7, Day 14 n	Day 21 + 2
Informed consent	X								
Inclusion/exclusion criteria	X	X							
Medical history	X	X							
Weight/height/BMI	X	X a							
Drugs of abuse screen/urine alcohol test/urine cotinine screen	X	X							
HIV/HCV/HBV serology	X								
Physical examination b	X	X	X	X	X	X	X		X
Concomitant medications	X	X	X	X	X	X	X	X	X
ECG	X c		X c	X d	X d	X d	X d		X d
Cardiac telemetry			X e	X e					

Assessment	Screening	In Clinic (CRU) Study Period						Return to CRU for PK Sample	Follow-up or Early Termination Visit
	Day -28 to -2	Day -1 (Admission)	Day 1 Baseline (Pre-dose)	Day 1 (Post dose)	Day 2	Day 3	Day 4 (Discharge)	Day 5, Day 7, Day 14 n	Day 21 + 2
ECHO f		X f				X f			
Vital signs	X	X	X g	X g	X g	X	X		X
Pregnancy test h	X	X							X
FSH i	X								
Clinical chemistry/hematology	X	X m		X	X	X	X		X
Urinalysis	X	X m			X	X	X		X
aPTT/PT	X	X m					X		X
Testosterone j		X m					X		X
Troponin I		X m					X		X
CK-MB		X m					X		X
Cystatin C and NGAL		X m					X		X
UACR	X	X m					X		X
Plasma for galidesivir PK analysis k			X k	X k	X	X	X	X	X
Urine for galidesivir PK analysis l			X	X	X	X	X		
AE assessment		X	X	X	X	X	X	X	X
Study drug dosing				X					

Abbreviations: AE = adverse event; aPTT = activated partial thromboplastin time; BMI = body mass index; CK-MB = creatine kinase-MB; CRU = clinical research unit; ECG = electrocardiogram; ECHO = echocardiogram; FSH = follicle-stimulating hormone; HBV = hepatitis B virus; HCV = hepatitis C virus; HIV = human immunodeficiency virus; NGAL = neutrophil gelatinase-associate lipocalin; PK = pharmacokinetic; PT = prothrombin time; UACR = urine albumin-to-creatinine ratio.

- a. Weight only.
- b. A physical examination consisting of the head and neck, skin, chest (lungs and heart), abdomen (gastrointestinal tract, liver, spleen and kidneys), back, musculoskeletal system, and neurologic system should be conducted at screening and on Day 4 prior to discharge. Breast and genitourinary system do not require examination unless the potential subject indicates a complaint or comorbidity that could result in exclusion. All other physical exams will be symptom directed. The site of infusion should be checked for any changes in skin.
- c. Three (3) serial ECGs will be performed at screening and baseline 1–3 minutes apart. Pre-dose ECG should be collected within  $\leq 2$  hours of the first dose.
- d. 12-lead ECGs will be conducted on Day 1 at 2 and 4 hours post dose (post start of the infusion) and on Day 2 at 24 hours post dose. An acceptable window is  $\pm 10$  minutes from the nominal time point. All subsequent ECGs are daily.
- e. Cardiac telemetry will be initiated  $\geq 2$  hours prior to administration of the dose and will continue for 24 hours after the infusion is started. Subjects may be disconnected for bathroom, hygiene needs, and for 20-minute periods 3 times a day for meals. In addition, subjects may be disconnected for 10 minutes every 2 hours while awake for mild physical exercise such as walking or calf exercises.
- f. The ECHO may be performed at any time from screening to Day -1 for eligibility determination. An ECHO should also be performed on Day 3. An acceptable window for the Day 3 ECHO is up until Day 4 discharge.
- g. Vital signs (except temperature) will be obtained pre-dose (within 2 hours of dosing) 1, 2, 4, and 8 hours post dose (post start of the infusion) on Day 1, at 24 hours post dose on Day 2 and once per day where indicated. Oral temperature will be obtained at 8 hours post dose on Day 1 and at 24 hours post dose on Day 2. Subjects should be rested for 10 minutes in the supine position prior to vital sign measurements.
- h. A serum pregnancy test will be administered at screening to all women; all other pregnancy tests performed during the study may be urine pregnancy tests.
- i. An FSH level will be measured in women who report that they have been postmenopausal  $\leq 2$  years.
- j. Free testosterone will be measured in male subjects.
- k. Plasma for PK galidesivir analysis will be collected pre-dose, 30 min (halfway through the infusion), 1 h (end of the infusion), 1.25 h, 1.5 h, 2 h, 3 h, 4 h, 6 h, 8 h, 10 h, 12 h, 16 h, 24 h, 36 h, 48 h, 60 h, 72 h, and 96 h following the start of the infusion. The pre-dose PK sample must be collected within  $\leq 1$  hour of the dose. Assessment windows around each PK draw will be  $\pm 2$  minutes for sampling times up to 2-hour post dose and from 2-hour post dose onward,  $\pm 10$  minutes while subject is confined in the unit. All sample times are from the start of the infusion.
- l. For the analysis of urinary excretion of galidesivir, an aliquot of urine will be collected pre-dose (0 hour) and all urine will be collected for the following post dose intervals: 0–12 hours, 12–24 hours, 24–48 hours, 48–72 hours, and 72–96 hours. All sample times are from the start of the infusion.
- m. Baseline for study post dose comparisons. NGAL, cystatin C, UACR, testosterone, troponin I, and CK-MB can be collected on Day -1 or Day 1 (pre-dose).
- n. Subjects will return to the CRU to have a plasma PK sample collected on Day 5 (+1), Day 7 (+1), and Day 14 ( $\pm 1$ ). This visit is intended to be a short visit (approximately 1-2 hours) and can take place at any time during the specified window. A plasma PK sample will also be collected at the follow-up visit on Day 21.

## Appendix 3: List of End of Text Outputs

List of End of Text Tables and Figures:		
Output	Title	Analysis Population
Section 14.1 – Disposition and Demographic Data		
Table 14.1.1	Summary of Subject Disposition	All Subjects
Table 14.1.2.1	Summary of Demographics	Safety
Table 14.1.2.2	Summary of Demographics	PK
Table 14.1.3	Summary of Study Drug Administration	Safety
Section 14.2 – Plasma Pharmacokinetic Data		
Table 14.2.1	Summary of BCX4430 Plasma Concentrations	Safety
Table 14.2.2	Summary of BCX4430 Plasma Pharmacokinetic Parameters	PK
Table 14.2.3	Summary of BCX4430 Urine Pharmacokinetic Parameters	PK
Table 14.2.3.1	Statistical Analysis of the Dose Proportionality: Power Model	PK
Table 14.2.3.2	Statistical Analysis of the Dose Proportionality: ANOVA Model of Pairwise Comparisons	PK
Figure 14.2.4	Plot of Mean ( $\pm$ SD) BCX4430 Plasma Concentrations vs Time on a Linear Scale	Safety
Figure 14.2.5	Plot of Mean BCX4430 Plasma Concentrations vs Time on a Semi-Log Scale	Safety
Figure 14.2.6	Plot of Median BCX4430 Plasma Concentrations vs Time on a Linear Scale	Safety
Figure 14.2.7	Plot of Individual BCX4430 Plasma Concentrations vs Time on a Linear Scale	Safety
Figure 14.2.8	Plot of Individual BCX4430 Plasma Concentrations vs Time on a Semi-Log Scale	Safety
Figure 14.2.9	Scatter Plot of Individual BCX4430 Plasma Pharmacokinetic Parameters	PK
Section 14.3 – Safety Data		
Table 14.3.1.1	Summary of Adverse Events	Safety
Table 14.3.1.2	Summary of Treatment Emergent Adverse Events by System Organ Class and Preferred Term	Safety
Table 14.3.1.3	Summary of Treatment Emergent Adverse Events by Relationship to BCX4430	Safety
Table 14.3.1.4	Summary of Treatment Emergent Adverse Events by Severity	Safety
Table 14.3.2	Listing of Serious Adverse Events	All Subjects
Table 14.3.3	Listing of Deaths	All Subjects
Table 14.3.4	Listing of Abnormal Laboratory Values	All Subjects
Table 14.3.5.1	Summary of Laboratory Results	Safety
Table 14.3.5.2	Summary of Laboratory Shifts from Baseline	Safety

Table 14.3.5.3	Summary of Treatment Emergent Graded Laboratory Toxicities	Safety
Table 14.3.6	Summary of Vital Signs	Safety
Table 14.3.7.1	Summary of 12-Lead Electrocardiogram Results	Safety
Table 14.3.7.2	Summary of QTcF Categorical Findings	Safety

